#### (2) Non-hematologic toxicity

- 1) Grade ≥4 non-hematologic toxicity. Note: Toxicities with no safety risk at the discretion of the investigator are excepted, such as grade 4 GGT increased and alkaline phosphatase (ALP) increased.
- 2) Grade 3 non-hematologic toxicity (including but not limited to hepatobiliary disorders). Note: Toxicities with no safety risk at the discretion of the investigator (such as grade 3 nausea, vomiting, diarrhea, asthenia, constipation, loss of appetite, mucositis, GGT increased, ALP increased) are not defined as DLT, but they will be defined as DLT when the toxicities do not recover to grade ≤2 within 7 days under the circumstance of symptomatic supportive treatment are permitted.

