Abnormal grade 4 laboratory test results that are not life-threatening judged by the investigator (such as grade 4 GGT increased and ALP increased).	Administration interruption until the toxicity is resolved to grade ≤2 or grade ≤1.  Resume the study treatment at the dose reduced by one level c after the toxicity is resolved to grade 2 (only when the investigator believes resuming the study treatment poses no safety risk to the subject) or grade ≤1 (the sponsor and investigator will decide whether to continue the administration after a comprehensive assessment of the benefits and risks).
Grade 4 Toxicities with no safety risk at the discretion of the investigator are excepted, such as grade 4 GGT increased and ALP increased.  Abbreviations: ALP = alkaline	Discontinue permanently.  phosphatase; DLT = dose-limiting toxicity; GGT = γ-

glutamyltransferase.

BB102 tablets/Phase I Protocol No.: BB102-ST-I-02

**Note:** a. Applicable to all hematologic toxicities (if a hematologic toxicity is related to other non-hematologic clinical events, refer to the rules for dose interruption, resumption and adjustment of non-hematologic toxicities).

B: The rules may be modified based on the previously obtained clinical trial data of BB102 tablets.

C: Available dose levels of BB102 tablets include 50 mg QD, 100 mg QD, 160 mg QD, 240 mg QD, 320 mg QD and 420 mg QD. If dose reduction is required at the starting dose level, the subject should discontinue the treatment permanently.

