## (3) Other conditions

1) The grade is elevated from baseline with clinically significant and/or unacceptable toxicity, which is judged as a DLT by the SMC.

- 2) Drug discontinuation lasting 7 days or more due to drug-related toxicity.
- 3) The dose received by the subject during the DLT observation period is less than 75% of the scheduled dose due to toxicities attributable to study drug, and the investigator believes that it should be considered as a DLT.

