# In the dose escalation trial, dose interruption, resumption and permanent discontinuation during the DLT observation period:

- No dose adjustment is allowed in the DLT observation period, but the doses may be interrupted, resumed and permanently discontinued.
- ➤ If several toxicities occur at the same time, dose interruption, resumption and permanent discontinuation should be carried out according to the most serious toxicity.
- (1) During the DLT observation period, if the subject develops DLT, the doses should be interrupted, and supportive treatment should be given as needed. The doses can be continued when the dosage has been administered before dose interruption is more than 75% of the scheduled dose, and the subject recovers to grade  $\leq 1$  or baseline (or, recovers to grade  $\leq 2$  and the investigator believes that there is no safety risk).
- (2) If the subject develops DLT again, the doses should be permanently discontinued, and unscheduled safety follow-up should be arranged until the toxicity is resolved or stabilized.
- (3) If the subject has other non-DLT toxicities, dose interruption needs to be determined according to the investigator's medical assessment, and supportive treatment will be provided as needed.

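### Protocol 4.1.1.4(2) ends the grade 3 no-safety-risk exemption after 7 days without recovery but sets no such limit at grade 4, so a persistent event can count less toward DLT at the higher grade.

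*Protocol*

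**What the plan says.** Section 4.1.1.4(2) of the protocol, with the same content in synopsis 1.3(2), has two items for drug-related non-haematologic toxicity in the DLT observation period.

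- Item 1 makes "Grade ≥4 non-hematologic toxicity" a DLT, with the note: "Toxicities with no safety risk at the discretion of the investigator are excepted, such as grade 4 GGT increased"; a rise in ALP is named alongside. Nothing is said about how long the exempted toxicity may last.
- Item 2 makes grade 3 non-haematologic toxicity a DLT and exempts toxicities that the investigator judges to carry no safety risk. GGT and ALP are listed again, with nausea, diarrhoea and others. This exemption is conditional: "they will be defined as DLT when the toxicities do not recover to grade ≤2 within 7 days", supportive treatment being permitted.

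Section 4.1.1.4(3) adds three further routes to a DLT:

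- a clinically significant and/or unacceptable rise in grade from baseline "which is judged as a DLT by the SMC";
- study drug stopped for 7 days or more because of drug-related toxicity;
- less than 75% of the scheduled dose received because of drug toxicity, together with the investigator's opinion that this is a DLT.

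On dosing during the DLT period, section 6.1.2 says: "If the subject has other non-DLT toxicities, dose interruption needs to be determined according to the investigator's medical assessment".

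**The concern.** A DLT definition should not count an event less as its grade rises. Here the two exemptions rest on the same investigator judgement and name the same two laboratory toxicities, yet only the lower grade carries a time limit.

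The DLT count is a primary endpoint of the dose escalation trial (7.1). It drives the 3+3 decisions (4.1.1.3), the MTD definition of DLT in at most 1/6 of subjects, and the rule for opening a dose in the expansion trial (4.1.2). Section 8.5 reuses the definition for adverse events of special interest in the expansion trial. An inconsistency in the definition therefore passes into each of these.

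**Working it through.** The protocol gives no figure to reproduce here. Section 10.1 states that the sample size was not estimated, and no rate is given for any DLT type. The check is a comparison of texts.

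**Step 1: the two exemptions side by side**

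| | Grade 3 (item 2) | Grade 4 (item 1) |
|---|---|---|
| Ground for exemption | Investigator judges no safety risk | Investigator judges no safety risk |
| Laboratory examples named | GGT, ALP | GGT, ALP |
| Recovery condition | Grade 2 or lower within 7 days, otherwise DLT | None |
| Example: GGT at that grade for 10 days, drug-related, judged no safety risk, dosed through | DLT under (2) | Not a DLT under (2) |

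**Step 2: do the criteria in 4.1.1.4(3) close the gap?**

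- SMC judgement needs no dose interruption, so it can capture the event, but it is discretionary and has no time trigger.
- The 7-day discontinuation criterion applies only if the drug is actually stopped that long. An exempted grade 4 event is a non-DLT toxicity, so under 6.1.2 interruption is the investigator's choice. A subject dosed through never triggers it.
- The 75% criterion needs lost doses and the investigator's opinion.

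Each may capture the event; none must.

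**Step 3: the recording rule.** Under the heading on change in severity in 8.1.1, a rise in grade closes the existing record and opens a new one, while a fall keeps the record at its highest grade. Read record by record, a grade 3 event that worsens to grade 4 before day 7 ends as a short grade 3 record. A later fall back to grade 3 opens no new grade 3 record. Worsening can thus take the event out of the 7-day rule.

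**Step 4: effect on a cohort decision.** Take one such subject who is not counted.

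- First three subjects: 1/3 if counted (enrol three more); 0/3 if not (proceed to the next dose).
- Six subjects, one other DLT already counted among the first three: 2/6 if counted (discontinue escalation); 1/6 if not (proceed, and meet the 1/6 limit).

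Since 1/3 = 2/6 > 1/6, each counted version fails the 1/6 limit used for the MTD and for opening expansion, and each uncounted version meets it.

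**Step 5: illustration with assumed rates.** Let p be the rate of counted DLTs and q the rate of additional subjects with a persistent, exempted grade 4 event. Both are assumptions. Under the 3+3 count alone, the probability of escalating at event rate x is

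E(x) = (1 − x)³ + 3x(1 − x)² × (1 − x)³.

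For p = 0.20, E = 0.512 + 0.197 = 0.709. With q = 0.10 also counted, E(0.30) = 0.343 + 0.151 = 0.494.

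| p | E(p), grade 4 events not counted | E(p+q), q = 0.05 | q = 0.10 | q = 0.20 |
|---|---|---|---|---|
| 0.10 | 0.906 | 0.814 | 0.709 | 0.494 |
| 0.20 | 0.709 | 0.600 | 0.494 | 0.309 |
| 0.30 | 0.494 | 0.396 | 0.309 | 0.172 |

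The table shows how sensitive the count is if such events occur and no other criterion captures them. It does not estimate how often they occur.

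**The case against.** The strongest reply is that the gap is narrow and partly covered. The event must be drug-related, reach grade 4, persist beyond 7 days, be affirmatively judged to carry no safety risk, and be dosed through or held only briefly. The SMC can still call it a DLT. Under 4.1.1.3 and 4.1.1.6 the SMC also decides on escalation from the safety data as a whole, in which a grade 4 event would be visible whatever its label. All of this stands. It limits the consequence, but it replaces a stated rule with discretion exactly where the grade 3 item has a rule.

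A sponsor might also mean to exempt isolated GGT or ALP rises at any duration. Item 2 does not fit that intent, because it counts persistent grade 3 GGT and ALP. It could also be argued that an event which passed through grade 3 has not returned to grade 2 in time and so falls under item 2. The text does not say so, and the recording rule in 8.1.1 points the other way.

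Three stronger readings are tempting, and the documents do not support them.

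- A reader might infer that the exemption falls on the toxicity most to be expected, since the liver is the main target organ in both animal species. GGT does not appear in section 1.5.3. In the 28-day rat study the ALP rise was not among the findings judged adverse; in the 28-day dog study ALP fell. Section 1.7 lists diarrhoea, asthenia, pyrexia, vomiting and nausea as the most common events with similar drugs. Bilirubin, ALT and AST are named in neither exemption.
- A reader might infer that such grade 4 events escape the DLT definition altogether. They escape criterion (2) only.
- A reader might see a contradiction with the dose-modification table in 6.1.2, which resumes grade 4 GGT or ALP one level lower and grade 3 at the original dose. That table governs the period after DLT observation and the expansion trial. It shows that grade 4 is treated as the worse event there, but it does not contradict the DLT rule.

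**Conclusion.** The concern holds in a limited form. As written, criterion (2) can count a persistent no-safety-risk toxicity at grade 3 and not count the same toxicity at grade 4. The criteria in 4.1.1.4(3) may capture it but do not have to.

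The size is one subject's status in a cohort of three or six: 0/3 instead of 1/3, or 1/6 instead of 2/6. That matters only if such an event occurs, is dosed through, and the SMC does not act. The documents give no frequency, so no expected effect on the trial can be stated. The 50 mg accelerated step is not affected at its trigger, because any drug-related toxicity of grade 3 or above already converts that group to 3+3.

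**What to change.** Reconcile items 1 and 2 of section 4.1.1.4(2), and the identical text in synopsis 1.3(2), so that the definition treats the two grades coherently and no event counts less toward DLT at the higher grade. Which condition should apply is a clinical decision for the sponsor and investigators. The reconciled text should also say how an event that moves between grade 3 and grade 4 is handled, given the recording rule in 8.1.1.

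The cost is one clause in two places, carried automatically into 8.5 by its cross-reference. The number of events counted as DLT may change slightly.

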## (3) Other conditions

1) The grade is elevated from baseline with clinically significant and/or unacceptable toxicity, which is judged as a DLT by the SMC.

- 2) Drug discontinuation lasting 7 days or more due to drug-related toxicity.
- 3) The dose received by the subject during the DLT observation period is less than 75% of the scheduled dose due to toxicities attributable to study drug, and the investigator believes that it should be considered as a DLT.

## 4.1.1.5 DLT evaluable subjects

If the dose received by a subject during the DLT observation period is less than 75% of the scheduled dose for reasons other than toxicities attributable to study drug, this subject should not be included into the final DLT analysis of this dose group or the overall groups. If the above situation occurs in any subject, the corresponding dose group needs to enroll one more subject for replacement to ensure the minimum required number of DLT evaluable subjects.

#### 4.1.1.6 SMC

The SMC should be composed of the sponsor (medical monitor, etc.), the investigator, the medical monitor of the Contract Research Organization (CRO), and other relevant personnel. The SMC meetings should be held as needed in the appropriate phase of the trial, e.g., before moving to the next dose group, when significant toxicity occurs, and after escalation to the maximum dose group. The SMC should discuss the obtained data such as subject safety, tolerability, PK, food effects, and preliminary efficacy through appropriate means (such as teleconferences, online conferences or emails, and if necessary, on-site meetings), and make a decision on whether to perform dose escalation or dose de-escalation, whether and how to adjust the escalation dose, whether to add dose groups, etc.

## 4.1.2 Expansion trial (expansion groups)

Based on the safety, tolerability, PK and efficacy data obtained in previous trials, 1 to 3 appropriate doses (e.g., 100 mg QD, 160 mg QD, and 240 mg QD) will be selected for the expansion trial.

The expansion trial can be initiated when the above doses are demonstrated to have a favorable safety in the dose escalation trial (i.e., the number of subjects experiencing DLT in the group is  $\leq 1/6$  of total subjects of the group), without waiting for the completion of the entire dose escalation trial.

Each expansion group will enroll 12 subjects to investigate the efficacy, safety and PK profiles of BB102 tablets. During the expansion trial, AEs meeting the definition of DLT will be regarded as AEs of special interest for safety assessment, thereby enriching the safety assessment data.

#### 4.2 Randomization and Blinding

## 4.2.1 Screening number

Patients must sign the ICF before they can be screened. The screening number is "XXYYY", where "XX" is the study site number, and "YYY" is the patient's serial number for signing the ICF. The first subject of site 01 is 01001, the third subject of site 02 is 02003, and so on. If a patient fails screening or withdraws from the trial, the patient's screening number can no longer be used, and patients withdrew from the study can no longer participate in the trial.

#### 4.2.2 Randomization method

This phase I trial is a non-randomized trial and no randomization will be performed.

### 4.2.3 Blinding

This phase I trial is an open-label trial involving dose escalation and expansion, and does not involve blinding.

### 4.2.4 Blind code preservation, unblinding and unblinding procedures

Not applicable.

## 4.3 Study Procedures

Throughout the Phase I study, all subjects need to receive study treatment, safety assessment, PK blood sampling and efficacy evaluation according to the visit schedule.

The tumor tissue specimens will be collected and preserved. For the specific collection, handling and storage methods, refer to the related standard operation procedure (SOP) of each study site. Computed tomography (CT) and other electronic documents should be saved on disc.

All laboratory tests should be carried out in laboratories recognized by study sites. Normal ranges of all laboratory test items and the updates during the trial should be collected and preserved.

If the investigator deems it necessary, each test item can be retested within the corresponding test time window and the retest data shall prevail.

#### **Tumor assessment:**

1) Imaging tests like computed tomography (CT) /magnetic resonance imaging (MRI) and other radiological examinations of chest, upper abdomen, lower abdomen, pelvic cavity and other positions will be performed. For patients with suspected or known brain metastasis, a radiological examination must be performed at screening/baseline, and contrast-enhanced MRI is preferred (for those allergic to contrast medium, CT/MRI plain scan is acceptable). If brain metastasis is confirmed at screening, the frequency of brain CT/MRI in the subsequent cycles should be kept consistent with the tumor assessment frequency specified in the study; if it is confirmed that there is no brain metastasis by brain CT/MRI at screening, brain CT/MRI

will be performed for confirmation if brain metastasis is suspected by the investigator later. For patients with bone metastasis symptoms, a bone scan must be performed at screening/baseline, and those with a positive result should receive contrast-enhanced MRI scan at the corresponding position for further confirmation. If bone metastasis is confirmed at screening, a bone scan or contrast-enhanced MRI (for those allergic to contrast medium, MRI plain scan is acceptable) will be performed for confirmation if progression of the pre-existing bone metastasis or new bone metastasis is suspected by the investigator later; if it is confirmed that there is no bone metastasis at screening, a bone scan or contrast-enhanced MRI (for those allergic to contrast medium, MRI plain scan is acceptable) will be performed for confirmation if bone metastasis is suspected by the investigator later. Tumor assessments will be performed according to RECIST v1.1. Tumor markers: During the corresponding visits for imaging tests, 4 mL of peripheral blood will be collected for the detection of tumor biomarkers, such as liver cancer [alpha-fetoprotein (AFP), carcinoembryonic antigen (CEA)], breast cancer [cancer antigen 15-3 (CA15-3)], ovarian cancer and endometrial cancer [carbohydrate antigen 125 (CA125)], prostate cancer [prostate specific antigen (PSA)], lung cancer [cytokeratin 19 fragment (CYFRA21-1)] and pancreatic cancer [carbohydrate antigen 242 (CA242)], which serve as auxiliary efficacy indicators.

- 2) If a subject received a CT/MRI or other radiological examinations within 4 weeks prior to the first dose and has not received any anti-tumor therapy since this tumor assessment, and at the investigator's discretion, the tumor assessment can be performed according to RECIST v1.1, this examination result can be used as baseline tumor assessment result (repeated examination is not necessary).
- 3) A tumor assessment will be performed at the end of Cycle 1, for which the time window is the end of the cycle ± 1 day. Thereafter, tumor assessments will be performed once every 2 cycles, for which the time window is the end of every 2 cycles ± 7 days [if a subject's assessment result is CR, PR or stable disease (SD), the subject can continue the treatment and continue to receive tumor assessments once every 2 cycles].
- 4) The radiological confirmation examination of CR or PR should be completed 4-8 weeks after the first evaluation of CR or PR.
- 5) For the end of treatment visit (EOT), the investigator will determine whether a tumor assessment is required according to the actual condition. If a tumor assessment has been performed within 2 months prior to EOT, it is not necessary to repeat the tumor assessment at EOT visit.
- 6) During the subsequent follow-up visits once every 8 weeks (±7 days) after the last dose, a tumor assessment will be performed for the subjects who are assessed as having no tumor progression in the previous assessment.

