#### **Composition of the low-fat meal:**

Total calories (kcal)	400-500	
Fat (g)	11-14	
Calories from fat (%)	25	
An example of a low-fat breakfast*	• Eight ounces milk (1 percent fat)	
	One boiled egg	
	One packet flavored instant oatmeal made with	
	water	

\*Note: 25% of calories are derived from fat. Substitutions can be made to this meal, if the content, volume, and viscosity are maintained. A registered dietician at the study site should determine the appropriate meal to be consumed, based on the fat and calorie requirements assigned to the patient for that treatment day. The start/stop time of meal consumption, and estimated % of test meal consumed (based on fat and caloric content), must be listed in the meal record eCRF for patients allocated in exploratory food effect group.

- For dose group A in the dose escalation trial, subjects will take BB102 tablets with water within 30 minutes following the meal on the other dosing days; no food is allowed within 1 h post-dose. Subjects will be on a normal diet.
- In the expansion trial, subjects will be fasted for at least 2 hours before dosing and take BB102 tablets with water; no food is allowed within 1 h post-dose. Subjects will be on a normal diet. Note: The administration method of the expansion trial may be adjusted according to the previously obtained food effect evaluation results of BB102 tablets.
- **4. Dosing frequency and cycles:** once daily in 21-day cycles (the dosing frequency and cycle setting may be adjusted according to the previously obtained clinical trial data of BB102 tablets).

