#### 5. Frequency of tumour re-evaluation

Frequency of tumour re-evaluation while on treatment should be protocol specific and adapted to the type and schedule of treatment. However, in the context of phase II studies where the beneficial effect of therapy is not known, follow-up every 6-8 weeks is reasonable. Smaller or greater time intervals than these could be justified in specific regimens or circumstances. The protocol should specify which organ sites are to be evaluated at baseline (usually those most likely to be involved with metastatic disease for the tumour type under study) and how often evaluations are repeated. Normally, all target and non-target sites are evaluated at each assessment. In selected circumstances certain non-target organs may be evaluated less frequently. For example, bone scans may need to be repeated only when complete response is identified in target disease or when progression in bone is suspected.

After the end of the treatment, the need for repetitive tumour evaluations depends on whether the trial has as a goal the response rate or the time to an event (progression/death). If 'time to an event' (e.g., time to progression, disease-free survival, progression-free survival) is the main endpoint of the study, then routine re-evaluation of protocol specified sites of disease is warranted. In randomised comparative trials in particular, the scheduled assessments should be performed as identified on a calendar schedule (for example: every 6-8 weeks on treatment or every 3-4 months after treatment) and should not be affected by delays in therapy, drug holidays or any other events that might lead to imbalance in a treatment arm in the timing of disease assessment.

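### For subjects who stop treatment without documented progression, the scan gap spanning discontinuation is nominally 8-14 weeks instead of 6, because the EOT scan may be skipped and follow-up scans are timed from the last dose

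*Protocol*

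**What the plan says.** Cycles are "once daily in 21-day cycles" (Protocol section 5.2). Section 4.3, Tumor assessment, sets the scan schedule:

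- Item 3, first scan: "A tumor assessment will be performed at the end of Cycle 1, for which the time window is the end of the cycle ± 1 day".
- Item 3, later scans: "tumor assessments will be performed once every 2 cycles, for which the time window is the end of every 2 cycles ± 7 days".
- Item 5, EOT: "the investigator will determine whether a tumor assessment is required according to the actual condition", followed by "If a tumor assessment has been performed within 2 months prior to EOT, it is not necessary to repeat the tumor assessment".
- Item 6, follow-up: "During the subsequent follow-up visits once every 8 weeks (±7 days) after the last dose", for subjects with no progression at the previous assessment.

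Flow-chart note 15 repeats items 3, 5 and 6; sections 4.3.4 and 4.3.5 repeat the EOT and follow-up rules. The EOT visit falls within 7 days of the last dose. Under the notes to section 4.3.5, follow-up scanning ends at new anti-tumor therapy or data cut-off, among other reasons. Section 4.7 puts the cut-off 8 weeks after the last subject starts treatment.

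PFS and DOR are among the primary endpoints of the expansion trial (section 7.2). Section 10.4.8 defines the PFS event as objective RECIST progression or death, and censors subjects with neither at the end of the trial at their last objective tumor assessment.

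**The concern.** Each rule is unremarkable alone. Together they let the interval between scans stretch exactly when a subject comes off drug. The EOT scan can be omitted for nearly everyone on schedule, and the 8-week follow-up clock restarts at the last dose, ignoring the time already elapsed since the last scan. The interval then depends on where in the scan cycle the subject happened to stop.

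Subjects who stop because of RECIST progression already have the scan that dates it, so they are unaffected. The issue concerns those who stop for toxicity, clinical deterioration, refusal or other reasons in section 3.3. For them, PFS and DOR rest on the next scan. A longer gap means a later recorded progression date, or no recorded progression if scanning ends first. At stake is the accuracy of descriptive PFS and DOR estimates in groups of 12.

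**Working it through.** The protocol states no figure for this gap, so there is nothing to reproduce. The inputs are those listed above.

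**1. Does the EOT waiver normally apply?** Two months is about 59-62 days.

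- Nominal interval plus latest EOT: 42 + 7 = 49 days, inside the waiver.
- Longest interval the two scan windows allow: 42 + 7 + 7 = 56 days, still inside.
- Both scan windows plus latest EOT: 42 + 14 + 7 = 63 days, outside.

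Only the extreme combination escapes. Read literally, the screening scan counts too: an expansion subject scanned 28 days before the first dose who stops before C1D21 reaches EOT at most 28 + 20 + 7 = 55 days later.

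**2. Gap spanning discontinuation.** Gap = (last scan to last dose) + (last dose to first follow-up scan).

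| | Last scan to last dose | Last dose to next scan | Gap |
|---|---|---|---|
| Nominal | 0-42 days | 56 days | 56-98 days = 8-14 weeks |
| All windows | 0-56 days | 49-63 days | 49-119 days = 7-17 weeks |

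If stopping is uniform within the 6-week interval, the nominal mean is 3 + 8 = 11 weeks.

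**3. Dating delay.** The gap is not itself the bias. The relevant quantity is the mean time from true progression to the scan that documents it. Assumptions: no progression at the last scan; exponential time to progression; stopping uniform over the 6 weeks; the subject stays in scan follow-up. The central median is 3.3 months, reported for fisogatinib in section 1.3. The range uses 2.6 months (median time to progression in one roblitinib group) and 4.1 months (PFS for H3B-6527), from the same section. Simulated mean delays in weeks:

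| Rule | 2.6 months | 3.3 months | 4.1 months |
|---|---|---|---|
| As written (no EOT scan, next scan 8 weeks after last dose) | 5.3 | 5.0 | 4.8 |
| Scan at EOT, then every 8 weeks | 4.0 | 4.0 | 4.0 |
| 6-weekly calendar kept from the last scan | 3.2 | 3.2 | 3.1 |

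Re-anchoring item 6 to the previous assessment gives a fixed 8-week grid. With hazard λ, the mean delay is 8/(1 − e^(−8λ)) − 1/λ. At 3.3 months the median is 3.3 × 30.4375/7 = 14.35 weeks, so λ = 0.693/14.35 = 0.0483 and the delay is 8/0.3205 − 20.70 = 4.26 weeks. At 2.6 and 4.1 months the formula gives 4.3 and 4.2. The gain over the current text is therefore about 0.8 weeks at 3.3 months, against 1.0 for a scan at EOT.

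**4. When the scan never happens.** If new therapy starts before the follow-up scan, scanning ends and the subject is censored at the old scan. The cut-off does the same. For the last-enrolled subject it falls 56 days after the first dose, while the earliest follow-up scan is 49 days after the last dose. That scan fits only if dosing ended within 56 − 49 = 7 days of starting.

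**The case against.** The strongest reply is that this is a scheduling preference, not an error. Most of its parts stand.

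- **Appendix I is not contradicted.** A reader might infer a breach because the appendix says "follow-up every 6-8 weeks is reasonable". That sentence concerns assessment on treatment in phase II studies and is followed by an allowance for other intervals. The on-treatment schedule of 6 weeks complies. For the period after treatment the appendix offers 3-4 months as an example, which the nominal 8-14 weeks does not exceed. Its call for timing unaffected by treatment events is aimed particularly at randomised comparisons, and this trial has no comparator.
- **The waiver is discretionary.** An investigator who suspects progression can still scan at EOT. The computed gap is what the text permits, not what every subject will have.
- **Only some subjects are affected,** and the documents give no basis for their number. Confirmation scans, due 4-8 weeks after a first response, shorten some gaps for responders.
- **Late dating is not universal.** It requires that the subject remain in scan follow-up. Section 10.4.8 handles discontinuation under a hypothetical strategy for DOR and uses a similar approach for other endpoints. If that means censoring at discontinuation, the consequence is again censoring at an old scan.
- **A bias that grows with dose is not shown.** One might infer it from more frequent toxicity stops at higher doses, but section 1.6 reports no clinical data on BB102 yet.

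What survives is narrower. The section 10.4.8 definitions count progression up to the end of the trial, PFS and DOR are primary in the expansion, and the interval depends on when the subject stopped for no stated reason.

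**Conclusion.** The point holds as a cheap improvement, not as a contradiction or a threat to the trial. For subjects who stop without documented RECIST progression, the permitted gap across discontinuation is nominally 8-14 weeks, mean 11 under uniform stopping, and 7-17 weeks with all windows, against 6 weeks on treatment. In those who stay in scan follow-up, mean dating delay is about 5.0 weeks as written and 4.0 with an EOT scan, under exponential progression with a 3.3-month median. In the others, progression may be missed and the subject censored at an old scan.

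A reader might set the 14-week gap beside a median PFS of 3.3 months and infer a large distortion. The calculation does not support that: the avoidable part is roughly a week on average, within an unquantified subset. The trial is descriptive and tests no hypothesis (section 10.3), so the effect is on the accuracy of PFS and DOR and their comparability with other trials, not on any error rate.

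**What to change.** Keep the EOT waiver. In item 6 of section 4.3, and in the matching text of section 4.3.5 and flow-chart note 15, time the first post-treatment scan from the previous tumor assessment. Suggested wording: *within 8 weeks (±7 days) of the previous tumor assessment, then every 8 weeks*. Nominally the scan then falls 2-8 weeks after the last dose (8 minus the 0-6 weeks already elapsed), so some progressions that would be lost to new therapy or cut-off are captured as well as dated earlier.

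The cost is one sentence in three places and at most about one extra scan per affected subject. The scan may not coincide with the survival follow-up visit. The change does not repair the short cut-off for the last-enrolled subjects: a scan at day 21 plus 56 days is day 77 of multiple dosing, beyond the 56-day cut-off. It alters no dosing or treatment rule.
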